6.3.2 Clinical Response Definitions

6.3.2.1 Clinical Response at the EOT and TOC Assessments

Clinical outcome assessments (see [Table 5](#)) will be made by the Principal Investigator at the EOT and TOC visits. Clinical response will be classified as cure, failure, or indeterminate based on clinical outcome. A favourable clinical response is “clinical cure”. A clinical failure occurring at an earlier time point will be carried forward to the TOC visit.

Table 5 Clinical Response Assessments at the EOT and TOC Visits

Outcome	Definition
Clinical Cure	Total resolution of all signs and symptoms of pneumonia (ie, CABP), or improvement ^a to such an extent that further antimicrobial therapy is not necessary
Clinical Failure ^b	Any of the following: * Persistence, incomplete clinical resolution, or worsening in signs and symptoms of CABP that requires alternative antimicrobial therapy * Treatment-limiting AE leading to discontinuation of the study treatment regimen, when patient required alternative antimicrobial therapy to treat the pneumonia * Death wherein pneumonia (ie, CABP) is considered causative
Indeterminate	Study data are not available for evaluation of efficacy, for any reason including treatment change prior to completing at least 48 hours of the study treatment regimen; death wherein pneumonia is clearly non-contributory, lost to follow-up, or extenuating circumstances preclude classification as a cure or failure

^a Clinical improvement includes the absence of fever (temperature $\leq 38^{\circ}\text{C}$ oral or $\leq 38.5^{\circ}\text{C}$ rectally or tympanically) for at least 24 continuous hours, with temperature recorded twice daily, in addition to a substantial improvement in signs and symptoms of CABP. Substantial improvement includes a return to pre-CABP baseline levels for patients with decreased pulmonary function (eg, patients with chronic obstructive pulmonary disease).

^b Clinical failures at EOT are carried forward to TOC.

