12.1.1.4 Clinically Evaluable (CE) Population

The CE Population will be a subset of the MITT Population and will include patients who meet the minimal disease criteria for CABP and all evaluability criteria, including patients

who received at least the pre-specified minimal amount of the intended-dose and duration of study drug therapy, for whom sufficient information regarding the infection is available to determine the patient's outcome, and for whom there are no confounding factors that interfere with the assessment of that outcome; patients with an atypical pathogen as a sole causative pathogen of the infection will be excluded from the CE Population.

In addition to meeting the above criteria, patients must meet the following specific conditions:

- At least 48 hours of study drug therapy received in order to be considered an evaluable clinical failure, unless deemed a clinical failure based on a treatment-limiting AE
- At least 72 hours of study drug therapy received in order to be considered an evaluable clinical cure
- At least 80% of the intended doses of study drug therapy received. Compliance is determined as the total number of received doses divided by the total number of intended doses based on the first and last date and time of study drug administration
- Clinical response assessment at TOC (8 - 15 days after EOT), or a clinical failure at EOT or at any time up to 15 days after EOT is allowed. For patients who died a 28 day window up to and including 28 days after EOT is allowed
- A patient with an indeterminate response at TOC is not included in the CE population unless the reason for the indeterminate response is "Death where CABP is non causative"
- Did not receive more than one dose of an alternative (non-study) systemic antimicrobial that was potentially effective for the treatment of CABP, for a reason other than treatment failure.

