12.2.2.2 Secondary efficacy endpoints

For each secondary efficacy outcome measure listed in [Table 10](#), a two-sided 95% CI for the difference between cure, success and favourable outcome rates (ceftaroline minus ceftriaxone) will be computed using the method proposed for stratified designs by Miettinen and Nurminen ([Miettinen O et al 1985](#)). Cochran-Mantel-Haenzel weights will be used for the stratum weights (defined by district) in the calculation of the CI.

Per-Patient Clinical Cure Rate at the TOC Visit in the MITT, mMITT and ME Populations

The per-patient clinical cure rate at the TOC visit in the MITT and mMITT Populations will be determined as:

$$\frac{\text{Number of patients with outcome=clinical cure}}{(\text{Number of patients with clinical cure} + \text{Number of patients with clinical failure} + \text{Number of patients with indeterminate})}$$

By definition, patients in the ME Population must have sufficient information for the determination of clinical outcome. Thus, the per-patient clinical cure rate in the ME Population is defined as:

$$\frac{\text{Number of patients with clinical cure}}{(\text{Number of patients with clinical cure} + \text{Number of patients with clinical failure})}$$

The number and percentage of patients classified as clinical cure, clinical failure, or indeterminate (by definition, indeterminates are excluded from the ME population) will be tabulated for both treatment groups.

A two-sided 95% CI for the difference in clinical cure rates (ceftaroline minus ceftriaxone) will be computed using the method proposed for stratified designs by Miettinen and Nurminen ([Miettinen O et al 1985](#)). Cochran-Mantel-Haenzel weights will be used for the stratum weights (defined by district) in the calculation of the CI.

Per-Patient Clinical Cure Rate at the EOT Visit in the MITT and CE Populations

The per-patient clinical cure rate at the EOT visit in the MITT and CE Populations will be determined to support the findings at the TOC visit. The number and percentage of patients classified as clinical cure, clinical failure, or indeterminate (by definition, indeterminates are excluded from the CE Population) will be tabulated for both treatment groups.

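### A death to which pneumonia contributed without being judged its cause has no single class in the primary endpoint, and the protocol does not settle whether an indeterminate death kept in the CE population stays in the cure-rate denominator

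*Protocol*

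**What the plan says.** The primary endpoint is the per-patient clinical cure rate at TOC in the CE population (Protocol synopsis and Section 12.2.2.1). The Principal Investigator assigns the outcome at EOT and TOC from Table 5 in Section 6.3.2.1. Deaths are handled in three places.

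- **Table 5, Clinical Failure:** "Death wherein pneumonia (ie, CABP) is considered causative".
- **Table 5, Indeterminate:** "death wherein pneumonia is clearly non-contributory, lost to follow-up, or extenuating circumstances preclude classification as a cure or failure".
- **Section 12.1.1.4, CE population:** being indeterminate at TOC removes a patient from CE, with a single exception, worded as "Death where CABP is non causative". The same section adds: "For patients who died a 28 day window up to and including 28 days after EOT is allowed".

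On the denominator, Section 12.2.2.2 gives cure/(cure + failure + indeterminate) for MITT and mMITT and cure/(cure + failure) for ME at TOC. In its text on the EOT analysis it says that "by definition, indeterminates are excluded from the CE Population". The protocol gives no formula for CE at TOC, which is the primary analysis.

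**The concern.** There are two linked problems.

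First, the two death criteria in Table 5 are not complements. Between a death that pneumonia caused and one to which it clearly did not contribute lies a death to which it contributed without being judged the cause. An example is a fatal cardiac event in a PORT class IV patient whose pneumonia is still active. Neither death criterion covers that case. The wording in Section 12.1.1.4 draws the line elsewhere: anything not causative is an indeterminate death, which takes in the whole middle group. Nothing in the protocol obliges such a death to be a failure.

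Second, once such a death is called indeterminate, its effect on the primary cure rate depends on the denominator. The passages bearing on that point in different directions: one keeps the patient in CE, and another says CE contains no indeterminates.

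At stake is whether an unfavourable outcome in an investigator-assigned primary endpoint is counted against the arm in which it occurs.

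**Working it through.** **1. Setting the death wordings side by side**

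| Role of pneumonia in the death | Table 5 death criteria | Section 12.1.1.4 label |
|---|---|---|
| Judged the cause | Failure | Does not fit the label |
| Contributed, not judged the cause | Neither criterion met | Fits the label: indeterminate, kept in CE |
| Clearly did not contribute | Indeterminate | Fits the label: indeterminate, kept in CE |

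The middle row is where the passages part. Outside the death criteria, Table 5 offers such a patient two routes. One is failure through persistence or worsening that requires alternative antimicrobial therapy, which a sudden death need not meet. The other is indeterminate because "extenuating circumstances preclude classification as a cure or failure".

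**2. Reproducing the plan's own figure**

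Inputs from Section 12.3: 85% cure in both arms, margin 10 points, power 90%, evaluability 77.5%. The two-sided 95% CI is from Section 12.2.2.1.

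- CE patients per arm: n = (1.960 + 1.2816)² × 2 × 0.85 × 0.15 / 0.10² = 267.9, so 268.
- Randomised per arm: 268 / 0.775 = 345.8, so 346, and 692 in total. This matches the protocol, and the point raised here does not change it.

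**3. Effect on one arm's cure rate**

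Take 228 cures in 268 CE patients (85.07%), and let g be the number of contributory, non-causative deaths among the 40 non-cures.

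- Kept in the denominator as non-cures: 228/268 = 85.07% for any g. The change is 0, the same as if they were failures.
- Dropped, g = 1: 228/267 = 85.39%, a change of 0.32 points.
- Dropped, g = 4: 228/264 = 86.36%, a change of 1.29 points.

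**4. Effect on the non-inferiority limit**

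This is an illustration using unstratified Miettinen-Nurminen 95% limits. The assumed counts are 218/268 cured on ceftaroline and 228/268 on ceftriaxone, chosen to lie close to the margin. The protocol gives no death count, so g is varied.

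| Deaths dropped: ceftaroline / ceftriaxone | Lower limit |
|---|---|
| 0 / 0 (counted as non-cures) | -10.12% |
| 1 / 0 | -9.80% |
| 2 / 0 | -9.48% |
| 4 / 0 | -8.83% |
| 1 / 1 | -10.10% |
| 4 / 4 | -10.04% |

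A death dropped from the ceftaroline arm alone moves the limit by about 0.3 points, which near the margin can change the conclusion. Equal numbers dropped from both arms hardly move it.

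**The case against.** The strongest reply is that Section 12.1.1.4 keeps these deaths in CE. The endpoint is a cure rate, a death is not a cure, and so the result is the same whether the label is failure or indeterminate. This stands as far as it goes: if retained deaths remain in the denominator, the effect is nil. But the protocol does not say that they do. The only formula it gives for an evaluable population omits indeterminates. That formula is for ME, a subset of CE, so a death retained in CE could reach ME as well. The statement that CE has no indeterminates appears in the EOT text, but it is worded as a property of the population.

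Two safeguards also count. Investigators and sponsor are blinded, and evaluability decisions are documented before codes are broken for analysis (Sections 5.4.1 and 5.4.2), so no mechanism for differential classification is shown. In MITT and mMITT, indeterminates are in the denominator, so such a death counts against cure there whatever its label.

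A reader might infer four stronger things that the protocol does not support.

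- **That the death has no category at all.** The residual clause on extenuating circumstances can take it. That clause does not make it a failure, however.
- **That Section 12.1.1.4 declares every non-causative death indeterminate.** It names a reason for a response already assigned. The wider reading is implied, not stated.
- **That the wording favours a non-inferiority conclusion.** This needs both a denominator that drops these deaths and an excess of them in the ceftaroline arm.
- **That each death is worth 1/268 = 0.37 points, or 1.5 points for four.** That is the effect of moving a patient between failure and cure, which neither wording does. Comparing a one-arm shift with the 10-point margin on the difference would also assume that all such deaths fall in one arm.

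**Conclusion.** The point holds as a contradiction in the definition of the primary endpoint, with a small and conditional numerical effect. A death to which pneumonia contributed but which it was not judged to cause meets neither death criterion in Table 5, fits the indeterminate label in Section 12.1.1.4, and so need not be a failure. Whether it then counts against the cure rate is left open between Sections 12.1.1.4 and 12.2.2.2.

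The effect is nil if such deaths are non-cures in the denominator. If they are dropped, it is about 0.32 points per death in one arm and about 1.3 points for four, largely cancelling when both arms are affected. The 268 CE patients per arm follow from Section 12.3. The number of such deaths and their split between arms are assumptions. The margin crossing shown above further assumes a result already close to -10% and deaths in the ceftaroline arm only.

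A statistical analysis plan could supply the CE formula. It would come too late to guide the investigators, who classify deaths from Table 5.

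**What to change.** Use one complementary classification of deaths throughout.

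- **Table 5:** a death is a clinical failure unless pneumonia was clearly non-contributory. The clearly non-contributory death remains the only indeterminate death.
- **Section 12.1.1.4:** replace the non-causative label with that same term, and use it in any case report form field that records the reason.
- **Section 12.2.2.2:** give the CE cure-rate formula at TOC. State that any indeterminate death retained in CE or ME stays in the denominator as a non-cure, and amend the statements that indeterminates are excluded from CE and ME, with the ME formula, to match.

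Aligning the labels alone would remove the mismatch in terms. It would not settle the denominator for the clearly non-contributory deaths that Section 12.1.1.4 still keeps in CE, so both changes are needed.

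The cost is wording. The sample size of 692 and the study procedures do not change. The downside is a slightly less favourable cure rate in both arms than if such deaths were dropped.

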6.3.2.2 Assessment of Clinical Relapse at the LFU Visit

Patients who were considered clinically cured at the TOC assessment will be reassessed at the LFU visit for evidence of continuing favourable response (no relapse). Patients with relapse of signs and symptoms of pneumonia (eg, new or increased cough, increased sputum production, purulent sputum or change in sputum character, dyspnoea, tachypnea, hypoxemia, auscultatory findings consistent with pneumonia, pleuritic chest pain) that require additional

antimicrobial therapy will be considered to have relapsed. Patients for whom data are unavailable at LFU will be assigned an “Indeterminate” response.

6.3.3 Radiographic Response Definitions

Radiographic outcome assessments (see [Table 6](#)) will be made at TOC and LFU visits, as outlined in the Schedule of Assessments (see [Table 1](#)). The TOC and LFU radiographic evaluations should be performed using the same modality (CXR or chest CT scan) as the baseline evaluation. Interpretation of radiographic studies and preparation of the radiographic report should be performed by an appropriately qualified (ie, certified or licensed according to applicable regional requirements) radiologist according to procedures outlined in [Appendix E](#). Investigators will use the radiographic report as the basis for assigning the outcome as a radiographic success, failure, or indeterminate.

Table 6 Radiographic Outcome Categories

Outcome	Definition
Radiographic Success	CXR or chest CT scan is resolved, improved, or stable compared to the baseline CXR or CT scan.
Radiographic Failure	CXR or chest CT scan has unequivocally worsened compared to the baseline CXR or CT scan.
Indeterminate	CXR or CT scan not performed, missing, or cannot be adequately interpreted to determine an outcome.

6.3.4 Microbiological Response Definitions

6.3.4.1 Per-Pathogen Microbiological Response

A microbiological outcome at the TOC visit will be determined in the mMITT and ME populations for each pathogen isolated at baseline (see

[Table 7](#)). Microbiological outcome categories are eradication, presumed eradication, persistence, presumed persistence, and indeterminate, as defined in the table below. Favourable microbiological outcomes are eradication or presumed eradication. Unfavourable microbiological outcomes are persistence or presumed persistence.

Table 7 Microbiological Outcome Categories

Outcome ^a	Definition	
Favourable	Eradication	An adequate source specimen ^b demonstrates absence of the original baseline pathogen.
	Presumed eradication	An adequate source specimen ^b was not available to culture and the patient was assessed as a clinical cure.
Unfavourable	Persistence	Source specimen demonstrates continued presence of the original baseline pathogen.
	Presumed persistence	An adequate source specimen ^b was not available to culture and the patient was assessed as a clinical failure.
Indeterminate	Indeterminate	An adequate source specimen ^b was not available to culture and the patient's clinical response was assessed as indeterminate.

^a The microbiological outcomes at TOC are only applicable to patients who are not clinical failures at EOT. Patients who are failures at EOT will have the corresponding microbiological outcome determined from EOT cultures and carried forward to TOC. If no EOT culture is available for patients who are clinical failures at EOT, then the microbiological outcome at TOC will be presumed persistence. Otherwise, the microbiological outcome at TOC will be determined from cultures obtained at the TOC visit window. If no culture is available in the TOC window then the microbiological outcome at TOC will be presumed from the clinical response (see [Table 5](#)) at TOC.

^b An adequate source specimen is defined as any sample that may yield the growth of a CABP pathogen eg, blood, respiratory specimens, or pleural fluid.

Note: For the special case of pneumococcal infection identified via a urinary antigen test only, the microbiological outcome will always be presumed from the clinical outcome (see [Table 5](#)), unless a post-baseline respiratory culture is positive for *Streptococcus pneumoniae*, in which case the microbiological outcome will be persistence. For patients with co-infection with an atypical, the outcome for atypical pathogens will be presumed from the clinical response (see [Table 5](#)).

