- l Determine patient's disease severity using PORT Score determination and confirm patient meets PORT Risk Class Determination III or IV (see [Appendix D](#))
- m Record resting vital signs, daily, including heart rate, blood pressure (after in a supine position for 5 min), respiratory rate and temperature (oral, rectal, or tympanic), while the patient remains on study treatment, at EOT and TOC. Measure the temperature in the a.m. and p.m. and record the patient's highest daily temperature.
- n Record oxygen saturation at baseline, daily while patient remains on the study drug therapy, at the EOT visit, and if medically indicated at the TOC visit
- o Obtain 12-lead ECGs:
- Baseline: three 12-lead ECGs separated by at least 1 minute, within a 15 minute period
 - Day 3 (± 1 day), EOT and TOC: one 12-lead ECG recording within 60 minutes of the end of Infusion 2
- p Chest X-ray / CT scan (see App. E) NOTE: these are not obtained at TOC or LFU for previous treatment failures
- q Laboratory tests include: haematology, clinical chemistry, PT/INR, PTT, RDW, MCV, reticulocyte count, haptoglobin, urinalysis and urine microscopy at times indicated in [Table 1](#), (see [Appendix G](#) and Laboratory Manual).
- r EOT Laboratory tests not performed if previous tests were within prior 24 hours
- s Additional Laboratory tests (blood): Reference: [Appendix G](#) and Laboratory Manual
- Baseline: c-reactive protein
 - Baseline and LFU: serology for atypicals
 - Baseline, EOT and TOC: direct Coombs
 - Arterial blood gas (ABG) to measure pH, P_aO_2 & P_aCO_2 , (according to investigator's judgment eg, hypoxic)
- t CLcr will be calculated at times indicated in [Table 1](#) and as medically indicated
- u Urine pregnancy test for women of child-bearing potential and those who are <2 years postmenopausal
- v EOT laboratory tests not performed if previous laboratory tests were within prior 24 hours
- v Results of *L. pneumophila* urinary antigen test (UAT) must be available before randomisation. Patients with a positive result are excluded from participation
- w Obtain sputum specimen, culture, perform Gram's stain and susceptibility testing (see Laboratory Manual):
- At baseline
 - Repeat if medically indicated.

- At EOT (if deemed a treatment failure),
 - At TOC (if deemed a treatment failure and was not previously categorized a failure),
 - At LFU if medically indicated (eg, patient experiencing a relapse)

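### A patient who fails after EOT can be scored as eradication from a TOC-window culture taken on rescue antibiotics (secondary microbiological endpoints only)

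*Protocol*

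**What the plan says.** Protocol section 6.3.4.1, Table 7 footnote a, sets three scoring routes for the microbiological outcome at TOC.

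- Failures at EOT: "Patients who are failures at EOT will have the corresponding microbiological outcome determined from EOT cultures and carried forward to TOC". If they have no EOT culture, the outcome is presumed persistence.
- Everyone else: "Otherwise, the microbiological outcome at TOC will be determined from cultures obtained at the TOC visit window".
- Fallback for that second group: "If no culture is available in the TOC window then the microbiological outcome at TOC will be presumed from the clinical response".

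Eradication in Table 7 needs only an adequate specimen that "demonstrates absence of the original baseline pathogen". It requires neither clinical cure nor freedom from non-study antibiotics, and section 6.3.4.2 adds no override for clinical failures.

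Section 12.1.1.4 foresees failures after EOT: "a clinical failure at EOT or at any time up to 15 days after EOT is allowed". It excludes patients for alternative antimicrobials only when these were given for a reason other than treatment failure. Section 6.3.2.1 defines the main type of failure by persistence, incomplete resolution or "worsening in signs and symptoms of CABP that requires alternative antimicrobial therapy". It says that clinical outcome assessments "will be made by the Principal Investigator at the EOT and TOC visits".

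On sampling, Table 1 footnote w asks for sputum "At TOC (if deemed a treatment failure and was not previously categorized a failure". Sections 6.3.1.1 and 6.3.1.3 say that sputum and blood are not taken at TOC in a patient already deemed a failure.

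**The concern.** A patient who is a cure at EOT, worsens afterwards and starts another antibiotic is a treatment failure. If a culture in the TOC window is then negative, the second drug may have cleared the organism, yet the rule records eradication and counts it as favourable for the study drug. With no culture, the same clinical course is presumed persistence and counts as unfavourable. The score then depends on whether a specimen happened to be taken, not on what the study drug did.

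The carry-forward rules also differ. For clinical response, section 6.3.2.1 carries any earlier failure forward to TOC. For microbiological response, footnote a does this only for failures at EOT. Read literally, even a positive culture taken when the patient failed is unused if it falls before the TOC window of 8 to 15 days after the last dose.

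At stake are the microbiological favourable rates at TOC, per patient and per pathogen, in ME and mMITT. They can be inflated, and a real difference between arms can be diluted. The LFU re-infection/recurrence analysis (section 12.2.2.2) takes ME patients with a favourable microbiological outcome at TOC, so it inherits the misclassified patients. Table 8 also requires a favourable clinical response at TOC for a recurrence, so these patients enter the denominator but cannot be events.

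**Working it through.** **The plan's own figure.** Section 12.3 gives cure rates of 85% in both arms, a 10% margin, 90% power and 77.5% evaluability; section 12.2 gives a two-sided 95% CI.

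- Evaluable per arm: (1.960 + 1.282)² × 2 × 0.85 × 0.15 / 0.10² = 268.
- Randomised per arm: 268 / 0.775 = 346; total 692.

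This matches the protocol. The figure concerns clinical cure and does not change with this point.

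**Tracing one patient.** Take a patient who is a cure at EOT, becomes a failure before or within the TOC window, and has started an alternative antimicrobial.

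1. Not a failure at EOT, so the EOT carry-forward does not apply.
2. Stays in CE, because the antimicrobial was given for treatment failure. With a qualifying baseline pathogen, the patient is in mMITT and ME.
3. TOC-window culture negative: eradication, favourable.
4. TOC-window culture positive: persistence, unfavourable.
5. No TOC-window culture: presumed persistence, unfavourable.

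No passage makes step 3 depend on whether the specimen was taken before or after the alternative antimicrobial.

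**Do the sampling rules prevent step 3?** In part.

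- Sections 6.3.1.1 and 6.3.1.3 send a known failure to step 5. They govern what is collected, not how a culture already in hand is scored.
- They do not cover pleural fluid. Table 1 and Appendix H section 1.6 allow a pleural specimen at TOC, although section 6.3.1.2 names only baseline to EOT.
- Appendix H section 1.6 asks for sputum and blood cultures in patients who were not failures at EOT and are failures now. Its exemption covers only failure at EOT. Table 1 footnote y (blood) is worded in the same way.
- A patient who fails within days 8 to 15 can start the new antibiotic before the specimen is taken.

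Pneumococcal cases identified by urinary antigen alone follow the clinical outcome, unless a later respiratory culture is positive (note to Table 7). They cannot be relabelled.

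**Direction and scale.** Let f be the true unfavourable rate in an arm and s the share of those patients relabelled as eradication, equal in both arms.

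- Observed favourable rate = 1 − (1 − s)f.
- Observed difference = (1 − s)d, where d is the true difference.

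With assumed true favourable rates of 85% (ceftriaxone) and 75% (ceftaroline), d = −10 points:

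| s | ceftriaxone | ceftaroline | observed difference |
|---|---|---|---|
| 10% | 86.5% | 77.5% | −9.0 |
| 25% | 88.75% | 81.25% | −7.5 |
| 50% | 92.5% | 87.5% | −5.0 |

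For patient numbers, assume that ME is 20% to 40% of the 268 CE patients per arm (54 to 107) and that 15% are failures in each arm. Failures in both arms together: 2 × 54 × 0.15 = 16 to 2 × 107 × 0.15 = 32. With s from 10% to 50%, 16.2 × 0.10 = 1.6 to 32.1 × 0.50 = 16 patients move to favourable. The protocol gives neither the ME share nor s, and the 15% is the CE planning value carried over to ME.

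**The case against.** The strongest reply is that the protocol already handles the obvious case. A patient who worsens a few days after the last dose and starts another antibiotic already meets the Table 5 definition of failure. Sections 6.3.1.1 and 6.3.1.3 then stop TOC sputum and blood sampling, and the fallback gives presumed persistence. This stands for patients recognised as failures before TOC. A reader might infer from the two formal assessment visits that most such patients are first classified at TOC. The protocol does not say so: section 6.3.2.1 carries earlier failures forward, and section 12.1.1.4 recognises failure at any time in the interval.

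Second, section 12.1.1.5 expects many or most patients to have no TOC specimen. Patients who stop early as failures have EOT assessments that day and are carried forward. The exposed group is therefore limited to cures at EOT who fail later and are nonetheless cultured. This also stands, and it makes the upper end of the ranges above unlikely.

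Third, preferring an observed culture to a presumed outcome is a legitimate choice, and details may be left to the SAP. The preference is reasonable in general, but it misleads when the observation follows a different effective drug. Footnote a also states a derivation rather than leaving one open, so the SAP would have to depart from it.

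A reader might also infer that the non-inferiority conclusion is at risk. It is not: the −10% criterion applies to clinical cure at TOC in CE, where these patients remain failures. The microbiological analyses have confidence intervals but no stated margin.

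**Conclusion.** The gap is real and narrow. Under footnote a as written, a negative TOC-window culture taken after alternative antimicrobials have started is eradication in a patient who failed after EOT, while no culture gives presumed persistence. The sampling rules reduce the number of such patients but do not settle how their cultures are scored.

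The effect is confined to the secondary microbiological endpoints at TOC (ME, mMITT) and the LFU subset derived from them. The primary endpoint and the sample size of 692 are untouched. The number of patients is probably small, and no inflation figure can be taken from the documents. The direction holds under one assumption: if the relabelled share is the same in both arms, any true difference shrinks by the factor 1 − s. The rule applies equally to both arms, so it does not in itself credit one treatment over the other.

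**What to change.** Add to Table 7 footnote a, for any patient who becomes a clinical failure after EOT and up to TOC:

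- A culture taken after the start of a potentially effective non-study antimicrobial may be scored as persistence but not as eradication.
- A post-baseline culture taken at the time of failure and before that antimicrobial counts, even if it falls before the TOC window.
- If there is no such culture, and none taken later shows persistence, the outcome is presumed persistence.
- Baseline cultures, and on-treatment cultures taken before the failure, do not count. Otherwise a positive baseline specimen would pass as documented persistence, or an early negative blood culture as eradication.

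The urinary-antigen rule can stay as it is. The wording of Appendix H section 1.6 and Table 1 footnote y must be reconciled with sections 6.3.1.1 and 6.3.1.3 on who is sampled at TOC. The Appendix H and Table 1 wording on pleural fluid must likewise be reconciled with section 6.3.1.2.

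The cost is a few sentences and one programming rule that compares culture dates with antimicrobial start dates. Table 1 already schedules cultures and concomitant medication; I assume that their dates are captured. The change affects scoring only. Its downside is a slightly lower microbiological favourable rate.
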